8.1.3. Subgroups

The primary efficacy endpoint will be summarized and analyzed by the following subgroups:

- Age (<65 years or ≥ 65 years)
- Gender (male or female)
- Race (White or Caucasian; Black or African-American; American Indian or Alaska native; Asian; Other)
- Baseline HbA_{1c} (>8.5% or $\leq 8.5\%$)
- Baseline eGFR (<60 or ≥ 60 mL min⁻¹ per 1.73 m²)
- Subject cardiovascular disease history or risk factors groups (Group 1; Group 2; or Group 3)
- Region (Europe, North America, or Asia Pacific)

8.2. SECONDARY EFFICACY ENDPOINT(S) AND ANALYSES

The key secondary efficacy endpoints include:

- Change in HbA_{1c} from baseline to week 24 in randomized subjects who have been prescribed insulin to control their diabetes.

- Change in body weight from baseline to week 48 in subjects with BMI $\geq 25 \text{ kg m}^{-2}$
- Change in SBP from baseline to week 24 in subjects with baseline systolic blood pressure $\geq 140 \text{ mm Hg}$

The exploratory efficacy endpoints include:

- Change in HbA_{1c} from baseline to week 24 in randomized subjects who have been prescribed sulfonylurea to control their diabetes
- Change from baseline in HbA_{1c} over time
- Change from baseline in FPG over time
- Change from baseline in body weight over time
- Change from baseline in SBP over time
- Requirement of additional anti-diabetic medications, including insulin; and time to first use of additional anti-diabetic medication
- Requirement of reduced anti-diabetic medications, including insulin dose over time
- Hospitalization for heart failure in all subjects and in subjects with a history of heart failure, identified on cardiovascular history CRF page.
- Time to hospitalization for heart failure in all subjects and in subjects with a history of heart failure
- Time to hospitalization for heart failure or cardiovascular death in all subjects and in subjects with a history of heart failure

8.2.1. Key secondary efficacy endpoints and analyses

A hierarchical testing procedure will be applied to these endpoints in the sequence of key secondary endpoints provided above. These key secondary endpoints will only be tested sequentially when significant treatment differences are established for the primary efficacy endpoint in the comparisons between the bexagliflozin and placebo groups.

Analysis for key secondary endpoints will be based on the ITT analysis set and repeated for the PP analysis set.

8.2.1.1. Change in HbA_{1c} from baseline to week 24 in randomized subjects who have been prescribed insulin to control their diabetes

This will be tested if the primary efficacy endpoint is significant. Change from baseline in HbA_{1c} at week 24 will be analyzed using the MMRM ANCOVA model with unstructured

covariance assumption. The model will include terms for treatment, baseline eGFR categories (<60 or ≥ 60 mL min⁻¹ per 1.73 m²), baseline BMI ($<$ or ≥ 25 kg m⁻²), and history of heart failure (yes or no), visit, treatment-by-visit interaction, and region as fixed effects and the corresponding baseline HbA_{1c} value as an additional fixed effect covariate. Data up to week 24 for subjects who have been prescribed insulin to control their diabetes will be used. Treatment comparison p-values and difference at week 24 will be estimated from the model, with the two-sided 95% CIs of the treatment difference also presented. If the model does not converge with the unstructured correlation assumption, an autoregressive AR(1) model will be used. If AR(1) does not converge, a compound symmetry model will be used.

Subgroup analysis will be conducted by baseline HbA_{1c} category and baseline eGFR categories.

8.2.1.2. Change in body weight from baseline to week 48 in subjects with BMI ≥ 25 kg m⁻²

This will be tested if the primary efficacy endpoint and the key secondary endpoint-change from baseline HbA_{1c}, overall and in subjects prescribed with insulin, are significantly different between bexagliflozin and placebo groups based on ITT analysis set. Change from baseline in body weight at week 48 will be analyzed using the MMRM ANCOVA model with unstructured covariance assumption. The model will include terms for treatment, visit, treatment-by-visit interaction, baseline HbA_{1c}, region, baseline eGFR categories (<60 or ≥ 60 mL min⁻¹ per 1.73 m²), baseline BMI ($<$ or ≥ 25 kg m⁻²), and history of heart failure (yes or no), insulin use or not as fixed effects and the corresponding baseline body weight value as an additional fixed effect covariate. Treatment comparison p-values and difference at week 48 will be estimated from the model, with the two-sided 95% CIs of the treatment difference also presented. If the model does not converge with the unstructured correlation assumption, an autoregressive AR(1) model will be used. If the primary hypothesis or treatment effect on HbA_{1c} for subjects prescribed with insulin is not significant, the nominal p-value will not be used for inferential purposes. Analysis will also be conducted for subjects who have been prescribed insulin or sulfonylurea to control their diabetes.

8.2.1.3. Change in SBP from baseline to week 24 in subjects with baseline SBP ≥ 140 mm Hg

This will be tested if the primary efficacy endpoint and the key secondary endpoints - change from baseline HbA_{1c} for subjects prescribed with insulin, and change from baseline body weight are significant. Change from baseline in sitting SBP at week 24 will be analyzed using the MMRM ANCOVA model with unstructured covariance assumption. The model will include terms for treatment, region, baseline eGFR categories (<60 or ≥ 60 mL min⁻¹ per 1.73 m²), baseline BMI ($<$ or ≥ 25 kg m⁻²), and history of heart failure (yes or no), insulin use or not, visit, treatment-by-visit interaction, baseline HbA_{1c} as

fixed effects and the baseline SBP value as an additional fixed effect covariate. Data used for this analysis includes change from baseline in SBP for all visits up to week 24 and for all subjects with baseline SBP ≥ 140 mm Hg. Treatment comparison p-values and difference at week 24 will be estimated from the model, with the two-sided 95% CIs of the treatment difference also presented. If the model does not converge with the unstructured correlation assumption, an autoregressive AR(1) model will be used. If the primary hypothesis on change of HbA_{1c}, treatment effect on HbA_{1c} for subjects prescribed with insulin, or change of weight from baseline to week 48 is not significant, the nominal p-value will not be used for inferential purposes. Analysis will also be conducted for subjects who have been prescribed insulin or sulfonylurea to control their diabetes.

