7. Female subjects of childbearing potential who are willing to use an adequate method of contraception and to not become pregnant for the duration of the study. Adequate contraceptive measures include, but are not limited to, oral contraceptives, intrauterine devices, Depo-Provera, Norplant, hormonal contraceptive implants, bilateral tubal ligation, partner with vasectomy, condom or diaphragm plus contraceptive sponge, foam, or jelly, and abstinence
 8. Subjects who are willing and able to return for all clinic visits and to complete all study-required procedures, including self-monitored blood glucose (SMBG) measurement, and take run-in medication, missing no more than one dose due to non-compliance
 9. Subjects who receive anti-hypertensive medications at a stable dosage for \geq 2 weeks prior to randomization
 10. Subjects who receive lipid modifying therapy on a stable regimen for 6 weeks prior to randomization
 11. Subjects who have seated SBP $<$ 170 mmHg and DBP $<$ 110 mmHg at screening.

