7.1 Screening Visit V1 (up to 3 weeks before run-in period)

The screening can be performed from 3 weeks to 3 days before the start of the run-in period for subjects. At the screening visit the staff at the investigational site will:

- Explain the content of the informed consent materials to the subject and collect signed informed consent
- Evaluate inclusion and exclusion criteria based on the information collected at the screening visit. Verify compliant fasting status as described in [Section 6.7.2.1](#).
- Obtain medical history and demographic information
- Perform a brief physical examination
- Measure vital signs, including blood pressures and heart rate
- Measure body weight and height
- Perform a 12-lead ECG measurement
- Draw serum sample for NT-proBNP evaluation within 1 h of the ECG measurement from Group 2 subjects with undocumented left ventricular ejection fraction (LVEF) or LVEF > 40%
- Draw blood if a minimum 10-h fast has been completed by the subject as described in [Section 6.7.2.1](#). The specific laboratory tests scheduled for this visit are listed in [Appendix 2](#).
- Collect clean-catch, mid-stream urine sample for urinalysis, and pregnancy test for all females

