Appendix 2 Schedule of Laboratory Tests

Procedure	Screening	Treatment						Follow up
	V1	V3	V5	V6	V8, 9, 10	V 12, 14, 16, 18, etc.	EV	FU
Time to Randomization Visit (weeks)		0	6	12	24, 36, 48	every 24 weeks	End of treatment	
Hematology ¹	X	X		X	X	X	X	X
Serum chemistry electrolytes ¹	X	X		X	X	X	X	X
Fasting Plasma Glucose ¹	X	X	X	X	X	X	X	X
HbA1c ¹	X	X	X	X	X	X	X	X
Lipids ^{1,2}	X	X		X	X	X	X	X
Urinalysis ³	X	X	X	X	X	X	X	X
UACR ⁴	X	X			X	X	X	
Infectious disease testing ⁵	X							
Urine pregnancy test (UPT) ⁶	X	X	X	X	X	X	X	X
PK sampling ⁷			X	X				
Biomarker sampling		X		X				
NT-proBNP sampling ⁸	X							

¹ Blood for clinical chemistry and hematology will be drawn after 10 h of fasting prior to breakfast (i.e. only water is allowed).

² LDL-C will be calculated by the Friedewald equation. At screening, the calculated LDL-C value is invalid by this equation and will be set as missing if triglycerides are > 400 mg/dL. Direct LDL-C will be determined in subjects whose baseline triglycerides are > 350 mg/dL. All subsequent LDL-C of these subjects will be determined by the same direct LDL-C measurements only.

³ Urine samples will be collected at all clinic visits. Glucose in the urinalysis results must be suppressed from the laboratory report so the dosing blind can be maintained. Testing strips with only the leucocytes and nitrate will be provided for immediate assessment at the sites.

⁴ UACR will be determined at screening V1, V3, and every 24 weeks until the end of treatment visit is conducted.

⁵ Infectious disease testing will be conducted at screening only. HIV testing will be conducted at screening in Canada.

⁶ UPT will be performed for WOCBP at all clinic visits. For surgically sterile or post- menopausal women, it will only be done at Visit V1.

⁷ Samples for the PK analysis will be drawn at weeks 6 and/or 12 from 240 subjects who consent to the PK study in participating trial centers.

⁸ Samples for NT-proBNP evaluation will be drawn within 1 h of the ECG measurement during the screening (V1) visit for Group 2 subjects with undocumented ejection fraction or documented left ventricular ejection fraction (LVEF) > 40%.

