6.2. KEY DEFINITIONS

6.2.1. Baseline Values

Baseline is defined as the last non-missing value on or prior to the day of the first dose of double-blind study medication. If the first dose date is missing, the last non-missing value on or prior to the randomization date will be used.

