laboratory reports so the sponsor, investigators, study coordinators, pharmacists, study subjects, and the adjudication committee members will remain blinded to the dosing assignment.

The baseline value for all laboratory tests will be the latest value obtained on or prior to Day 1. Change from baseline for all continuous parameters will be calculated as the post-baseline value minus the baseline value. All continuous variables will be summarized by number of subjects [n], mean, SD, Q1, median, Q3, minimum and maximum and categorical variables will be summarized by frequency and percentage.

Observed values (in SI units) and change from baseline over time will be summarized by treatment arm. Laboratory data will be classified as low, normal, or high relative to the parameter's reference range. Laboratory abnormalities for each treatment will also be summarized with shift tables for selected parameters.

For hematology, chemistry, and serum lipids, columns will be included for normal ranges and individual abnormal laboratory values will be flagged and clinical significance will be indicated.

Urine albumin/creatinine ratio (UACR) will be summarized and analyzed separately. Descriptive statistics for geometric mean, geometric coefficient of variation (gCV), median, Q1, Q3, minimum, and maximum of UACR values will be presented at screening, baseline, and all post-baseline scheduled visits for all subjects and for baseline macroalbuminuria subjects ($>300 \text{ mg g}^{-1}$). UACR data is left-skewed and will be natural log transformed first. Change in log transformed UACR from baseline to week 24 will be analyzed by ANCOVA model. The fixed effect will include region, baseline HbA_{1c} level as continuous variable, region, baseline eGFR categories (<60 or $\geq 60 \text{ mL min}^{-1} \text{ per } 1.73 \text{ m}^2$), baseline BMI ($<$ or $\geq 25 \text{ kg m}^{-2}$), history of heart failure (yes or no), insulin use or not, and treatment. The log transformed baseline values will be used as covariate. Analysis will be repeated for baseline macroalbuminuria subjects. LS means for each treatment will be estimated at week 24. The adjusted geometric mean ratio of relative change from baseline in UACR (the ratio of the week 24 geometric mean and baseline geometric mean) and the corresponding two sided 95% CI by treatment arm will be calculated as the antilog of the LS mean and 95% CI of log transformed values, converted to percentage.

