9.5. VITAL SIGNS

Vital signs will be measured at the screening visit (Week -2 to -5), at week 0, 6, 12, 24, 36, 48 from screening to week 48, at every 24 weeks after week 48 to end of study, at end of treatment visit and follow up (4 weeks after end of treatment visit) visit.

Measurements of vital signs will include measurement of supine, sitting and standing blood pressure (BP) measurements, and heart rate. Only the BP measured in the sitting position will be used to determine eligibility. Orthostatic systolic and diastolic BP will be calculated as supine measurement - standing measurement.

For BP, pulse rate, and respiration rate, observed values and change from baseline will be summarized by treatment arm and nominal visit using descriptive statistics (n, mean and median, standard deviation, Q1, and Q3, minimum and maximum). For BP, supine, sitting, standing, and orthostatic BP will be summarized. Summary will also be conducted for subjects who have been prescribed insulin or sulfonylurea to control their diabetes.

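### The SBP key secondary and the UACR analysis adjust for one pre-dose reading although two are collected; adding the screening reading would bring a modest gain in precision at almost no cost

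*Combined protocol and SAP*

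**What the plan says.** SAP 6.2.1 sets one baseline for every endpoint: "Baseline is defined as the last non-missing value on or prior to the day of the first dose of double-blind study medication". SAP 9.4 repeats the rule for laboratory tests. A screening value therefore becomes baseline only when no later pre-dose value exists.

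**SBP.** The third key secondary endpoint (SAP 8.2.1.3) uses data that "includes change from baseline in SBP for all visits up to week 24 and for all subjects with baseline SBP" of at least 140 mm Hg. The MMRM has terms for treatment, region, eGFR category, BMI category, heart failure history, insulin use, visit, treatment-by-visit and baseline HbA1c as "fixed effects and the baseline SBP value as an additional fixed effect covariate". The SBP imputation model in SAP 8.2.1.4 draws on earlier time points from baseline onward and does not name screening.

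**UACR.** The week 24 ANCOVA in SAP 9.4 has a similar list of terms, and "The log transformed baseline values will be used as covariate". Screening UACR appears only in the descriptive summaries.

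**Two pre-dose readings exist for each.** The V1 activities in protocol 7.1 include "Measure vital signs, including blood pressures and heart rate", and SAP 9.5 states: "Vital signs will be measured at the screening visit (Week -2 to -5), at week 0, 6, 12, 24, 36, 48". Protocol Appendix 2 states: "UACR will be determined at screening V1, V3, and every 24 weeks until the end of treatment visit is conducted". Both V1 values are needed for eligibility: inclusion criterion 11 ("Subjects who have seated SBP" below 170 mm Hg at screening) and exclusion criterion 14 (UACR above 2000 mg/g at screening).

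**The concern.** SBP and UACR vary from visit to visit within a subject, so a single reading measures the usual level with error. A second reading taken 2 to 5 weeks earlier helps separate the usual level from that day's noise. Protocol 5.2.4 does not permit antihypertensive treatment to be adjusted during screening and run-in, so the two SBP readings are close to replicates. The SBP model already carries region, insulin use and HbA1c, yet omits a second pre-treatment measurement of the outcome itself.

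What is at stake is precision. SBP is the last confirmatory test in the hierarchy and is run in a subset. Neither document gives an SD, effect size, subset size or power for it; protocol 9.6.1 says only that a high proportion of subjects should qualify. UACR is a safety endpoint outside the hierarchy, so for it only the width of the interval is affected.

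**Working it through.** The plan states no figure on this point, so there is nothing to reproduce. The correlations, SD, effect and subset size below are assumptions. The 2:1 allocation, the visit times, the 140 and 170 mm Hg limits and the significance level (one-sided 0.025 in the SAP, two-sided 0.05 in the protocol) come from the documents.

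**Step 1: equal correlation r among V1, V3 and week 24.** Residual variance, as a share of total, is 1 − r² with V3 alone and 1 − 2r²/(1 + r) with both readings. The relative reduction is r²/(1 + r)².

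| r | Reduction by formula | SBP, simulated with V3 ≥ 140 and V1 < 170 (SD 16, mean 135 / 140) |
|---|---|---|
| 0.4 | 8.2% | 7.3% / 6.8% |
| 0.5 | 11.1% | 9.9% / 9.3% |
| 0.6 | 14.1% | 12.5% / 11.9% |
| 0.7 | 17.0% | 15.4% / 14.7% |

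For SBP this gives about 7-15%. For log UACR at r = 0.7, 0.8 and 0.85 the formula gives 17.0%, 19.8% and 21.1%, without modelling the eligibility limit on V1 UACR.

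**Step 2: correlation that falls with time.** V1 and V3 are 2-5 weeks apart; week 24 is 24 weeks from V3 and 26-29 weeks from V1. Let a = corr(V3, week 24), b = corr(V1, week 24) and c = corr(V1, V3). The reduction is the squared partial correlation of V1 with week 24 given V3:

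(b − ac)² / [(1 − a²)(1 − c²)]

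- (0.5, 0.45, 0.6): (0.45 − 0.30)² / (0.75 × 0.64) = 0.0225 / 0.48 = 4.7%
- (0.5, 0.4, 0.6): (0.40 − 0.30)² / 0.48 = 2.1%
- (0.6, 0.55, 0.7): 5.2%
- (0.7, 0.65, 0.8): 4.4%
- (0.8, 0.77, 0.82): 11.0%

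Of 14 such combinations tried, 12 lie between about 2% and 7%; the largest is 11%.

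**Step 3: confidence interval width.** Width scales with √(1 − g), where g is the reduction. At g = 2%, 1 − √0.98 = 1.0%. At g = 15%, 1 − √0.85 = 7.8%.

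**Step 4: power, illustration only.** Assume 700 subjects in the subset at 2:1, a difference of 3 mm Hg, SD 16 and r = 0.5 between V3 and week 24.

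- Residual SD with V3 alone: 16 × √(1 − 0.25) = 13.86.
- SE: 13.86 × √(3/700 + 1.5/700) = 1.111.
- Power: Φ(3/1.111 − 1.96) = Φ(0.740) = 77%.
- With V1 added, SE is multiplied by √(1 − g): g = 2.1% gives 77.9%, 4.7% gives 79.0%, and 9.8% (equal correlation, within the simulated 9.3-9.9%) gives 81.1%.

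**The case against.** The strongest reply is that nothing here is wrong. Adjusting for one prespecified last pre-dose value is standard, unbiased and applied consistently throughout the SAP. That stands.

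The second reply concerns size. Equal correlation is the favourable case. V1 and V3 are close together under fixed antihypertensive treatment, whereas protocol 5.6 restrains changes to blood pressure medication only for the first 12 weeks of treatment. The V1-V3 correlation therefore plausibly exceeds the V3-week 24 correlation, which makes V1 more redundant. This also stands, and it is why the SBP range starts at 2%. The very bottom is nevertheless a steep case: it has the correlation with week 24 drop from 0.5 to 0.4 over only 2-5 extra weeks. A smoother assumption, constant visit noise plus exponential decay over the actual schedule, gave about 4.5-10%.

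Third, the SBP model has no baseline-by-visit term. If correlations decay, a single common V1 slope over weeks 6-24 need not deliver the full gain at week 24. That is fair, and the fix allows for it.

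A reader might infer that the plan gives up 7-20% of the variance for nothing. The documents do not support that. The range requires equal correlations that they never state, and its upper end comes from UACR, not SBP. Nor is the screening reading thrown away: it is the fallback baseline, and screening UACR is summarized. A reader might also think that selecting subjects on the same V3 reading makes the loss worse. It does not: in simulation, selection at 140 mm Hg alone left the gain unchanged, and the V1 limit of 170 mm Hg lowered it slightly.

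**Conclusion.** The point holds as a missed efficiency gain. The SBP MMRM and the UACR ANCOVA each omit a pre-treatment reading of their own outcome that is collected for essentially every subject. Neither bias nor type I error is affected by the omission.

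For SBP, adding V1 would cut residual variance by roughly 2-15%: about 7-15% under equal correlation of 0.4-0.7 with the V1 limit, and about 2-7% in most cases where correlation decays. For log UACR the reduction is up to about 20% under equal correlation of 0.7-0.85, and less if correlation decays. All of these rest on assumed correlations and ignore the other covariates in the models. The power figures also depend on the assumed SD, effect and subset size.

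A prespecified pre-randomization covariate introduces no bias, preserves type I error and, in a large sample, cannot increase residual variance. So the change is worth making even at the low end of the range.

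**What to change.** Before unblinding:

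- SAP 8.2.1.3: add V1 sitting SBP as a covariate in the MMRM, preferably with a V1-by-visit term so that the week 24 slope is not forced to equal the earlier ones.
- SAP 8.2.1.4: add V1 sitting SBP to the predictors in the SBP imputation model.
- SAP 9.4: add log V1 UACR to the ANCOVA.
- State how the model treats a subject whose V1 value is missing or already serves as baseline under SAP 6.2.1.
- Keep the last pre-dose value as baseline for change scores and for defining the 140 mm Hg and macroalbuminuria subsets.
- Record the change in SAP section 12, which already lists covariate changes from the protocol.

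The cost is one covariate per model, or one per visit with the interaction. No new data are needed, and few values should be missing because both V1 readings are used for eligibility.

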8.2.1.4. Sensitivity analysis

Same sensitivity analysis as described in section 8.1.2 for HbA_{1c} in randomized subjects will be used for subjects who have been prescribed insulin to control their diabetes. For other secondary analyses of body weight and SBP, missing data will be imputed via multiple imputations, following which the MMRM will be repeated on the complete datasets with results combined across complete datasets using standard multiple imputations techniques. Imputation steps include:

- a. Create monotone missing data as step a of section 8.1.1 with 100 imputed datasets;
- b. Regression approach under MAR will be used to generate complete datasets. The predictors for the regression imputation model at any time point will be region, baseline eGFR (≥ 60 or < 60 mL min⁻¹ [1.73m]⁻²), baseline BMI ($<$ or ≥ 25 kg m⁻²), and history of heart failure (yes or no), insulin use or not, baseline HbA_{1c}, treatment, and values at all previous time points, including baseline. Values at each visit will be imputed sequentially. The first imputed values for subjects in bexagliflozin arm will be penalized by the mean improvement of bexagliflozin on SBP at week 24 (i.e. the mean change from baseline at week 24) or on body weight at week 48 (i.e. the mean change from baseline at week 48). Imputed values for subjects in placebo will not be penalized. Imputed values after the first missing value will be penalized through regression on first penalized value.
- c. Imputed datasets will be analyzed and results combined as in step c in section 8.1.1.

